CONFIDENTIAL

 This material is the property of the NYU School of Medicine and Langone Health
 Do not disclose or use except as authorized in writing by the study sponsor

2.3	October 1, 2019	Inclusion/Exclusion criteria have been changed to enhance study recruitment within the safety parameters of the research.
2.4	November 11, 2019	The exclusionary medication list has been changed to reflect only the limitations put in place by the FDA; the other medication types have been removed to avoid redundancy.
2.5	December 10, 2019	Medical management has been removed from the 1-day, 4 weeks+1 day and 9-week visits because no study drug will be dispensed at the aforementioned time points. The C-SSRS will no longer be administered at the 1-day and 4-weeks+1-day visits. The study figure has been revised to reflect these changes.
2.6	January 10, 2020	Drinking criteria has been changed from 10 heavy drinking days to 8 heavy drinking days in order to facilitate recruitment efforts and the attainment of target enrollment numbers.
2.7	July 26, 2020	Option for remote e-consent was added; option to complete initial portion of screening visit remotely added; reimbursement schedule altered to reflect two-part screening visit option; consent updated to include risk of elevated liver enzymes; recruitment dates were updated; reference to COVID-19 safety procedures SOP was added
2.8	September 26, 2020	Website recruitment materials added
2.9	10/30/2020	Changed heavy drinking inclusion from 8 heavy drinking days to 6 heavy drinking days
3.0	February 15, 2021	Removed exclusion of drugs that are weak-moderate 3A4 substrates Clarified exclusion criterion #8 (Significant laboratory abnormalities, including significantly impaired liver function, serious abnormalities of complete blood count or metabolic panel). Added a new exclusion for Type I Diabetes, per the DSMB's review of risks associated with cannabis use and development of ketoacidosis in Type I Diabetes.
3.1	July 15, 2021	Added to the procedure section 8 which states that study team may ask for release of health information if it is helpful or requested by the participant.

CONFIDENTIAL

 This material is the property of the NYU School of Medicine and Langone Health
 Do not disclose or use except as authorized in writing by the study sponsor

A PHASE I/II RANDOMIZED, DOUBLE-BLIND, PLACEBO-CONTROLLED TRIAL OF CANNABIDIOL FOR ALCOHOL USE DISORDER

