6.2 Exclusion Criteria

An individual who meets any of the following criteria will be excluded from participation in this study:

- 1) Current alcohol withdrawal (CIWA-Ar score >7)
- 2) Exclusionary medical conditions (e.g. current severe alcohol withdrawal requiring medical hospitalization, significantly impaired liver function, Type I Diabetes)
- 3) DSM-5 diagnosis of schizophrenia, schizoaffective disorder, bipolar disorder
- 4) High risk of adverse emotional or behavioral reaction based on investigator's clinical evaluation (e.g., evidence of serious personality disorder, antisocial behavior, serious current stressors, lack of meaningful social support)
- 5) Current significant suicidality (assessed using the C-SSRS), any suicidal behavior in the past 12 months, or any history of serious suicide attempts requiring hospitalization, or current significant homicidality
- 6) History of severe Traumatic Brain Injury (LOC > 24 hours)
- 7) DSM-5 diagnosis of current mild cannabis use disorder and/or moderate or severe substance use disorder for a substance other than alcohol or nicotine
- 8) Significant laboratory abnormalities, including significantly impaired liver function*, serious abnormalities of complete blood count or metabolic panel
- 9) Active legal problems likely to result in incarceration within 12 weeks of treatment initiation
- 10) Pregnancy or lactation
- 11) Current use of exclusionary medications, including cannabinoids; treatments for addictions including alcohol; moderate to strong inhibitors of CYP3A4 or CYP2C19; medications metabolized primarily by CYP3A5, or CYP3A7; and medications with a narrow therapeutic index which are substrates of CYP3A4, UGT1A9, UGT2B7, CYP2C8, CYP2C9, CYP2C19, CYP1A2, or CYP2B6.
- 12) Allergy to any ingredient of the study compound.
- 13) Current treatment for AUD, with exception of AA/12-step treatment
- 14) No inpatient psychiatric treatment in the last 12 months, with the exception of detox and extended Emergency Department stays
- 15) A positive urine drug screen for THC, cocaine and/or opioids at screen

*Significantly impaired liver function will be operationalized as alanine aminotransferase (ALT), aspartate aminotransferase (AST), or alkaline phosphatase (Alk Phos) $> 2.5 \times$ upper limit of normal (ULN), or Total bilirubin $> 2.0 \times$ ULN in the absence of Gilbert's syndrome.

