6.6 Participant Withdrawal or Termination

6.6.1 Reasons for Withdrawal or Termination

Participants are free to withdraw from participation in the study at any time upon request. An investigator may terminate participation in the study if:

- Any clinical adverse event (AE), laboratory abnormality, or other medical condition or situation occurs such that continued participation in the study would not be in the best interest of the participant
- The participant meets an exclusion criterion (either newly developed or not previously recognized) that precludes further study participation
- The participant fails to adhere to protocol requirements

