8.3.1 Screening

Option 1: In-person Screening Visit (T0)

- Obtain informed consent of potential participant verified by signature on written informed consent for screening form.
- Review medical and psychiatric history to determine eligibility based on inclusion/exclusion criteria.
- Review concurrent medications to determine eligibility based on inclusion/exclusion criteria.
- Perform medical examinations needed to determine eligibility based on inclusion/exclusion criteria.
- Obtain demographic information, alcohol, drug, and tobacco use history
- Collect urine for urine drug analysis, urinalysis, urine pregnancy test
- Collect blood for LFTs, complete blood count, serum chemistries, serum pregnancy test

Schedule study visits for participants who are eligible and available for the duration of the study

Option 2: Two-part Remote and In-person Screening Visit (T0a/b)

Part a: Remote Screening

- Obtain informed consent of potential participant verified by signature on written informed consent for screening form.
- Review medical and psychiatric history to determine eligibility based on inclusion/exclusion criteria.
- Review concurrent medications to determine eligibility based on inclusion/exclusion criteria.
- Obtain demographic information, alcohol, drug, and tobacco use history
- test

Part a: In-person Screening

- Perform medical examinations needed to determine eligibility based on inclusion/exclusion criteria.
- Collect urine for urine drug analysis, urinalysis, urine pregnancy test
- Collect blood for LFTs, complete blood count, serum chemistries, serum pregnancy
- Schedule study visits for participants who are eligible and available for the duration of the study

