8.5 Prohibited Medications, Treatments, and Procedures

Treatment with medications including cannabinoids; treatments for addictions including alcohol; moderate to strong inhibitors of CYP3A4 or CYP2C19; medications metabolized primarily by CYP3A4, CYP3A5, or CYP3A7; and medications with a narrow therapeutic index which are substrates of UGT1A9, UGT2B7, CYP2C8, CYP2C9, CYP2C19, CYP1A2, or CYP2B6 will not be permitted unless discussed with and approved by the PI.

9 Definitions of Key Terms

An adverse event (AE; also referred to as an adverse experience) is any untoward medical occurrence associated with the use of a drug (pharmaceutical investigational product) in humans, which does not necessarily have a causal relationship with that treatment. An AE can therefore be any unfavorable and unintended sign (e.g., an abnormal laboratory finding or test result), symptom, disease, accident, or worsening (increase in severity or frequency) of a pre-existing abnormality, temporally associated with the use of the drug, whether or not considered related to the drug. An AE can arise from any use of the drug (e.g., off-label use, use in combination with another drug and from any route of administration, formulation, or dose, including overdose).

A serious adverse event (SAE) is an adverse drug or biologic or device experience occurring during any study phase (i.e., screening, admission, treatment, or follow-up), and at any dose of the study drug, comparator or placebo, that results in one or more of the following criteria:

- Results in death
- Is life-threatening*
- Requires in-patient hospitalization (i.e., admission) or prolongation of existing hospitalization

CONFIDENTIAL

This material is the property of the NYU School of Medicine and Langone Health
Do not disclose or use except as authorized in writing by the study sponsor

- Results in persistent or significant disability** or incapacity
- Is a congenital abnormality or birth defect (in an offspring)

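### The entry rule (6.2, exclusion 11) and the on-study rule (8.5) treat CYP3A4 substrates differently, and nothing at screening triggers the PI approval that 8.5 requires

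*Combined protocol and SAP*

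**What the plan says.** Two operative sections of the protocol list the medications of concern.

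- **Section 6.2, exclusion 11**, governs entry. On CYP3A metabolism it bars "medications metabolized primarily by CYP3A5, or CYP3A7; and medications with a narrow therapeutic index which are substrates of CYP3A4", followed by the other narrow-index enzymes.
- **Section 8.5** governs treatment during the study. It names "medications metabolized primarily by CYP3A4, CYP3A5, or CYP3A7" and, separately, "medications with a narrow therapeutic index which are substrates of UGT1A9, UGT2B7, CYP2C8, CYP2C9, CYP2C19, CYP1A2, or CYP2B6". All the listed medications "will not be permitted unless discussed with and approved by the PI".

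Three other places bear on how these rules work together. Section 8.3.1 describes the medication check at screening: "Review concurrent medications to determine eligibility based on inclusion/exclusion criteria". Section 8.4 has concomitant prescription and non-prescription medications recorded on the CRFs. Section 25.3 counts any noncompliance with the protocol as a deviation, reportable to the NIAAA Program Official and, under its guidelines, to the local IRB.

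**The concern.** Apart from CYP3A4, the two lists carry the same items, so they read as one list meant to apply at entry and during treatment. CYP3A4 sits in a different clause in each section, and the set of drugs covered changes with it. Staff who apply 6.2 and 8.3.1 exactly as written can enrol someone whose existing medication 8.5 does not allow without a further step that the screening procedure does not mention.

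The stakes are in trial conduct. The drug-interaction safeguard depends on which section is being read. Avoidable deviations can arise in participants who were enrolled correctly. Decisions on the same drug can differ between participants according to whether anyone consulted 8.5.

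**Working it through.** No arithmetic applies. The check is an item-by-item comparison of the two current lists.

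| Item | 6.2, exclusion 11 (entry) | 8.5 (on study) |
|---|---|---|
| Cannabinoids; addiction treatments | Listed | Listed |
| Moderate or strong CYP3A4 or CYP2C19 inhibitors | Listed | Listed |
| Metabolised mainly by CYP3A5 or CYP3A7 | Listed | Listed |
| Metabolised mainly by **CYP3A4** | **Not listed** | **Listed** |
| Narrow-index substrates of **CYP3A4** | **Listed** | **Not listed** |
| Narrow-index substrates of UGT1A9, UGT2B7, CYP2C8, CYP2C9, CYP2C19, CYP1A2, CYP2B6 | Listed | Listed |
| Exception on PI approval | None stated | Stated for the whole list |

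The difference in coverage is the placing of CYP3A4. There is none on inhibitors: exclusion 11 bars "moderate to strong inhibitors of CYP3A4 or CYP2C19" and 8.5 uses the same terms.

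For CYP3A4 substrates, three cases follow:

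1. **Mainly CYP3A4-metabolised, index not narrow.** Eligible under exclusion 11. Under 8.5, not allowed without PI approval. Here 8.5 is the stricter rule.
2. **Mainly CYP3A4-metabolised, index narrow.** Barred at entry, and not allowed on study without PI approval. Both sections cover it.
3. **Narrow index, a CYP3A4 substrate but not mainly metabolised by CYP3A4.** Barred at entry. Not restricted by 8.5 on that ground. Here 8.5 is the looser rule.

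For case 1, the next question is whether the approval would necessarily be in place by the first dose. Section 8.3.1 ties the medication review to the eligibility criteria, which this person passes. Section 8.5 requires discussion and approval but does not say when, by what procedure, or where it is recorded. The baseline visit (8.3.2), at which the first dose is given, lists no check against 8.5. So nothing in the text ensures the approval. If it was not obtained, the participant is out of compliance with 8.5 from the first dose, and 25.3 makes that a deviation.

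The version history at the front of the protocol has this entry for version 3.0: "Removed exclusion of drugs that are weak-moderate 3A4 substrates". It describes a past change and is not itself an error. It is consistent with exclusion 11 having been revised without a matching edit to 8.5, but that is an inference.

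**The case against.** The strongest answer is that the sections do different jobs. One decides who enters; the other governs what may be taken during treatment. An entry filter can coexist with a stricter on-study rule that has a PI gate: a person in case 1 is eligible, the PI discusses and approves the drug, and both sections are satisfied. Case-by-case approval is what 8.5 provides for, and is not a harm in itself.

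Much of this stands, and it rules out several stronger readings that a reader might infer:

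- **That 8.5 bans these drugs outright.** It does not; the restriction is lifted by PI approval.
- **That every such participant is in breach from the first dose.** Only one for whom approval was not obtained.
- **That affected participants will be withdrawn and lost from the primary analyses.** Section 6.6.1 lists "The participant fails to adhere to protocol requirements" as a reason for which an investigator may end participation, so termination is discretionary, and taking an approved drug is not a failure to adhere. Section 7.1.9 does limit the primary analyses to those completing 8 weeks, but a loss by this route needs approval to be missed or refused, the investigator to choose termination, and this to happen before T7. The documents do not suggest that sequence is likely. The completers rule is a separate matter.
- **That a definite number is affected.** Assuming that 5% to 20% take such a drug gives 0.05 × 40 = 2 to 0.20 × 40 = 8 participants, but nothing in the documents anchors those shares. The result would also count users of a drug type, not deviations or lost data.

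Two things survive. The gate works only if something prompts its use, and the screening procedure does not. And a deliberately stricter on-study rule would not explain case 3, where 8.5 is the looser one. Section 6.6.1 also allows termination for a newly developed exclusion criterion, which may partly cover a case 3 drug started on study, but that too is discretionary and does not make it a restricted medication under 8.5.

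**Conclusion.** The point holds as a misalignment between two current rules, in both directions. It rests on the wording of 6.2, 8.3.1 and 8.5 alone and needs no assumption about how often such drugs are used. Noncompliance from the first dose is possible for a correctly enrolled participant, on the condition that PI approval was not obtained.

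The size is modest. No power, alpha or sample-size figure is affected, and no effect on the analysis sets can be shown. The number of participants concerned cannot be derived from the documents; it would have to come from the trial's medication records. It still merits correction because it concerns an operative eligibility and drug-interaction rule. This review takes no position on which list is right.

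**What to change.** 1. Reconcile 6.2 exclusion 11 and 8.5 to one medication list, applied at screening and during treatment, covering both case 1 and case 3. The sponsor decides its content. If a difference between entry and on-study rules is intended, say so and give the reason.
2. State in 8.5 when any PI approval must be obtained relative to the first dose or to the start of a new drug, and where it is recorded. Add the corresponding check to 8.3.1.
3. From the concomitant-medication CRFs, list participants enrolled under one rule who did not comply with the other, noting whether PI approval was documented.

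The cost is a wording amendment, with the IRB review that section 24.2 requires for any amendment, and one pass through medication records that 8.4 already has collected. No new data collection and no change to the analysis are needed.

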11.1 Solicitation of AEs

At all follow-up visits occurring after study medication has been administered, the SAFTEE questionnaire [124] will be used to assess AEs through the following three prompts:

"Have you had any physical or health problems since our last visit?"

"Have you noticed any changes in your physical appearance since our last visit?"

"Have you cut down on the things you usually do because of not feeling well physically since our last visit?"

If the subject responds "yes" to any of these questions then the following question will be asked:

CONFIDENTIAL

This material is the property of the NYU School of Medicine and Langone Health
Do not disclose or use except as authorized in writing by the study sponsor

“Could you describe in more detail what this effect means to you?”

The presence or absence of specific AEs should not be solicited from subjects.

11.2 Preplanned Hospitalization or Procedure

During the study, if a subject has a hospitalization or procedure (e.g., elective surgery) that was due to a preexisting condition that has not worsened since enrollment in the study (i.e., since the subject [or the subject's legal representation] signed the informed consent), the hospitalization or procedure is considered a therapeutic intervention and not the results of an AE. However, if the event/condition worsens during the study, it must be reported as an AE (or SAE, if the event/condition results in a serious outcome, such as hospitalization).

11.3 Reports of Cancer

Cancer is no longer considered an FDA criterion for an SAE (unless an event occurs with a serious outcome). If a new diagnosis of cancer has a serious outcome, then the reporting time frame for an SAE (48 hours) must be met. Progression of disease is not considered new cancer and is therefore not an AE.

11.4 Specific guidelines for assessing laboratory values as adverse events

Any laboratory abnormality, including leukopenia, absolute neutropenia, or thrombocytopenia, will not be considered an AE unless this abnormal laboratory value results in clinical sequelae, such as infection, bleeding, or an intervention. If an abnormal laboratory value results in a clinical event, then the clinical event, not the abnormal laboratory value, must be recorded as an AE. The clinical event must be reviewed to determine if it meets the criteria for an SAE.

12 Assessment of Adverse Events

The following definitions, developed in accordance with the US Code of Federal Regulations (CFR) and the International Committee on Harmonization (ICH), will be used for the purpose of identifying AEs in this clinical study.

12.1 Expectedness

Unexpected: An AE is considered unexpected if it is not listed in the Investigator Brochure (IB) or is not listed at the specificity or severity that has been observed, or not previously observed in animal toxicity studies for psilocybin. Unexpected also refers to AEs that are mentioned in the IB as occurring with a class of drugs or as anticipated from the pharmacologic properties of the drug, but are not specifically mentioned as occurring with psilocybin.

12.2 Severity

The determination of severity must be made with the appropriate involvement of a medically qualified investigator. The investigator will evaluate the severity of each AE using the following three terms and definitions:

Minimal: single occurrence that is not distressing and does not limit activities

Mild: multiple occurrences, awareness of sign or symptom but easily tolerated, usually does not require intervention or limit activities

Moderate: discomfort sufficient to cause interference with normal activities; intervention may be needed

Severe: incapacitating, with inability to perform normal activities; treatment or other intervention usually needed

12.3 Relatedness

This category provides the opportunity to indicate the reasons for suspecting a drug-related effect. If no such effect is suspected, check “No.” The following reasons for possible relationship to drug are to be assessed by the medically qualified investigator.

CONFIDENTIAL

This material is the property of the NYU School of Medicine and Langone Health
Do not disclose or use except as authorized in writing by the study sponsor

Dose-response: indicates that the intensity of the event is related to the dosage level.

Timing of onset: is used if the onset of the event has some regular relationships to drug administration (e.g., it always occurs 1 hour after taking the drug).

Known drug effect: is another reason for suspecting a drug relationship.

The relationship of each AE to study drug will be assessed using the following terms and definitions:

Probable (must have first two): This category applies to AEs that are considered, with a high degree of certainty, to be related to the study drug. An AE may be considered probable, if:

- It follows a reasonable temporal sequence from administration of the drug.
- It cannot be reasonably explained by the known characteristics of the subject's clinical state, environmental or toxic factors, or other modes of therapy administered to the subject.
- It follows a known pattern of response to the suspected drug.

Possible: This category applies to those AEs in which the connection with the study drug administration is possible. An AE may be considered possible if, or when, any of the above reasons have been selected.

Unrelated: This category is applicable to those AEs that are judged to be due only to extraneous causes (e.g., disease, environment, etc.) and do not meet any of the criteria for a possible drug relationship.

The determination of the relationship of the AE to the use of the study drug(s) rests on careful medical consideration of the PI.

13 Monitoring Adverse Events

The investigator will follow all AEs until the event is resolved, stabilized, or the subject is lost to follow-up. Relevant clinical assessments and laboratory tests may be performed as determined by the PI or a qualified designee, appropriate medical intervention should be provided and, if necessary, the subject may be excluded from additional treatment with the study drug.

Any actions taken and follow-up results must be recorded on the appropriate page of the CRF and in the subject's source documentation. Follow-up laboratory results should be filed with the subject's source documentation.

For all AEs that require the subject to be discontinued from the study, relevant clinical assessments and laboratory tests will be repeated as clinically appropriate, until final resolution or stabilization of the event(s).

14 Known Potential Toxicities of Study Drug

Overall, no preclinical results have been identified that preclude the development of cannabidiol for the treatment of alcohol use disorder, or suggest that serious AEs are likely in clinical studies. Refer to the IB for toxicology findings and information on AEs observed to date.

15 Other Significant Adverse Events

Should any AE occur that is considered significant, but does not meet the criteria for an SAE, the CRC and PI should be notified immediately.

16 Reporting Procedures

